Randomized trial of holding vs. continuing incretin-based therapies before upper endoscopy

Principal Investigator:

[name].

Email: [contact]

Address: [name]

Background:

Incretin-based therapies include GLP-1 receptor agonists (GLP-1RAs) and dual GLP1-RA and gastric inhibitory polypeptide (GIP) agonists. These drugs are commonly prescribed for diabetes and more recently, their use has risen exponentially as a primary therapy for weight loss. These medications can decelerate gastric emptying and diminish bowel motility by inhibiting peristalsis at the GLP-1 receptors situated in myenteric neurons. Therefore, there exists a theoretic potential for gastroparesis, retained gastric contents, perioperative regurgitation, and pulmonary aspiration syndrome, and this is a concern for anesthesiologists and patients taking these medications.

The American Society of Anesthesiologists recently released a consensus-based statement that recommends patients on daily dosing hold incretin-based therapy the day of the procedure, and those on weekly dosing hold the medication a week before the procedure. The evidence for these recommendations is based on retrospective studies and case reports, and therefore the conclusions may be overly prescriptive. Furthermore, holding incretin-based therapy poses a risk for worsening diabetes control and more importantly, could cause unnecessary delays in care if a patient's procedure is postponed because they failed to hold the medication based on the recent recommendations (1-3).

Study Objective:

To assess whether holding incretin-based therapy before endoscopy reduces the likelihood of clinically relevant Residual Gastric Volume (RGV).

Hypothesis:

Holding incretin-based therapy is non-inferior to continuing incretin-based therapy for reducing the risk of clinically relevant RGV.

Study design:

Randomized Non-Inferiority Controlled Trial.

Blinding:

Single-blind: endoscopist and anesthesia team will be blinded to study group assignment.

Primary Outcomes:

The primary outcome is clinically significant residual gastric volume defined as a composite of the following variables:

- Residual gastric volume that precludes adequate endoscopic examination
- Residual gastric volume that necessitates premature termination of the endoscopy procedure
- Need for endotracheal intubation due to stomach contents.

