 - For patients who are not scheduled via the above route, a letter of invitation will be sent to the patient from the physician completing the procedure through the US mail or MyChart.
- Patient consent
 - Interested patients in the clinic setting will be given the option to complete a research encounter during the same day, including in-person consent if interested, or complete the process remotely over the phone and through MyChart Electronic consent, or DocuSign.
 - Patients who are not identified in clinic but through chart review will receive a phone call and phone encounters will be completed with interested potential participants and will include an explanation of the study and the consent process (phone scripts attached). MyChart Electronic consent process or DocuSign will be used to send the study consent to the participants.
- After obtaining consent, the patient information will be entered into the REDCap which will give the patient a REDCap serial number.

- A randomization tool in the REDCap will determine the intervention (The randomization table of allocation will be completed by a statistician on REDCap to ensure concealed allocation).
- The patient will be informed about the intervention during the clinic visit by a study member (not the endoscopist) or over the phone.
- A few days before the intervention, the patient will receive a call as a reminder of the intervention and instruction from a study member (not the endoscopist).
- On the endoscopy day, the proceduralist and anesthesia team will be blinded to the patient's group assignment. To ensure that blinding is maintained, a sticker will be placed on the patient physical chart to remind the provider to avoid asking about the study intervention.
- A research coordinator/investigator will confirm intervention compliance and record the variables of interest for the study.
- Information will be directly entered into the Redcap data collection sheet or recorded on a physical paper-based collection sheet and transferred immediately to Redcap on the same day. The physical sheets will be shredded on the day of the procedure.
- A phone call to the patient within the first week after the procedure to follow up and exclude aspiration events. If patient cannot be contacted, then a member of the study team will review patient records to identify any emergency department visits or hospitalizations related to a post-procedure aspiration event.

Electronic Consent operation

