Date of birth, gender, race, body mass index (BMI), type of incretin-based therapy used, incretin therapy dose, pre-endoscopy clinical symptoms, presence of diabetes, last HbA1c if available, detailed endoscopic reports, gastric residual content on endoscopy, and RGC-related events as described above. Please refer to the data collection sheet for details of the variables above.

Study Statistics

The Statistics will be done with the help of a Cleveland Clinic statistician. Data will be extracted in deidentified form directly from Redcap for analysis.

Once data has been collected, we will use STATA version 14.1 (STATA Corp, College Station, TX, USA) for statistical analysis. We will use statistics of central tendency (mean, median, and mode) for most values. Data normality will be tested using Kolmogorov-Smirnov test. We will use Pearson’s chi-square tests for categorical variables and T-test for continuous variables. A P-value of < 0.05 will be considered significant for all statistical analyses. The primary outcome will be calculated using chi-square or Mann-Whitney test. For the primary outcome, an intention-to-treat analysis will be utilized.

Interim Analysis and Data Monitoring Committee (DMC)

The study DMC will include the following: The gastroenterology program director at Weston, a gastroenterologist, and a Cleveland Clinic statistician. Meetings will be held at 20%, 50, and 100% of recruitment to ensure data security compliance, appropriate rate of recruitment, and study adverse events monitoring. A report of each meeting will be sent to the IRB. The DMC will not be blinded for study groups. Interim analysis will be conducted after 20 and 50% of recruitment on the second DMC meeting, and the study will be stopped if inferiority is confirmed.

Data Security

Data, including patient information and consent, will be stored electronically in the Redcap system\DocuSign which is password-protected and on the secure Cleveland Clinic network. If physical paper sheets were used, the physical paper sheets' information would be transferred to Redcap and shredded on the day of data gathering.

Possible Harm to Subjects and Adverse Events

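### The role that checks compliance also records the outcome variables, and the protocol does not say who classifies the primary composite or whether aspiration follow-up is blinded

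*Combined protocol and SAP*

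**What the plan says.** The Blinding section reads "Single-blind: endoscopist and anesthesia team will be blinded to study group assignment". It mentions no one else. Study Operation then sets out four things that bear on this point.

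- Patients learn their arm: "The patient will be informed about the intervention during the clinic visit by a study member (not the endoscopist) or over the phone". A reminder call follows a few days before the procedure, again from someone other than the endoscopist.
- On the day, "a sticker will be placed on the patient physical chart to remind the provider to avoid asking about the study intervention".
- Also on the day, "A research coordinator/investigator will confirm intervention compliance and record the variables of interest for the study". Study Variables lists among the data "gastric residual content on endoscopy, and RGC-related events as described above", together with the endoscopic reports.
- Within a week, a call to the patient looks for aspiration events. If the patient cannot be reached, a study team member reviews the records. No blinding is stated for either route.

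Three of the four components under Primary Outcomes are "Residual gastric volume that precludes adequate endoscopic examination", "Residual gastric volume that necessitates premature termination of the endoscopy procedure" and "Need for endotracheal intubation due to stomach contents". The fourth is aspiration that leads to longer observation, unplanned treatment or admission. The protocol gives no criteria for adequacy, early termination or need for intubation, does not say who decides that a component has been met, and describes no blinded adjudication.

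**The concern.** The blinding is there to protect an outcome that depends on judgement. Whether the stomach contents prevented an adequate examination, whether they forced an early stop, and whether they were the reason for intubation are all decisions that can be nudged by knowing the arm. The plan leaves three routes by which that knowledge could reach the outcome data.

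1. The role that records outcomes also asks about compliance, with no stated order and no separation of the two tasks.
2. The follow-up that establishes late aspiration, part of the primary composite, is done by the study team without stated blinding.
3. The sticker stops providers from asking, but the supplied text does not show that patients are told not to volunteer their arm.

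The direction of any shift cannot be predicted. Possible Harm to Subjects and Adverse Events describes a theoretical risk from continuing, which could make a recorder readier to count events in that arm. The same section says there is no strong evidence for that risk, and the Background suggests that the guidance to hold may go too far, which could pull the other way.

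**Working it through.** **Who knows the arm, and who touches each outcome field**

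| Step | Who | Blinding stated? |
|---|---|---|
| Tells the patient the arm; reminder call | Study member, not the endoscopist | No |
| Confirms compliance on the day | Coordinator/investigator | No; the task reveals the arm |
| Performs the procedure; decides adequacy, termination, intubation | Endoscopist and anesthesia team | Yes |
| Records the study variables | Coordinator/investigator, the same role | No |
| Classifies the composite as met or not | Not stated | Not stated |
| One-week aspiration call or record review | Study team | No |

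The clinical decisions in the third row are made by blinded people. The gap lies in the last three rows: the step from what happened in the room to a yes or no in the dataset, and the ascertainment of late aspiration.

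**Scale**

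Inputs from Sample Size Determination: 120 patients, 60 per group; margin 3 percentage points; one-sided 95% confidence; 80% power; Farrington-Manning score test; increased residual gastric volume in 5-7% of users and under 0.5% of non-users.

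The plan's sample size is checked first. With p_C = 0.07 (continue), p_H = 0.005 (hold) and margin m = 0.03:

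- n per arm = [(z_0.95 × s0 + z_0.80 × s1) / (m − (p_H − p_C))]²
- s1 = √(0.005 × 0.995 + 0.07 × 0.93) = 0.265
- s0 uses the rates fitted under a difference of exactly 3 points, 0.0658 and 0.0358, giving s0 = 0.310
- Denominator: 0.03 + 0.065 = 0.095
- n = [(1.645 × 0.310 + 0.842 × 0.265) / 0.095]² = 59.5, rounded up to 60; power at 60 per arm is 80.4%

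The stated 60 per group reproduces at 7% versus 0.5%. A literal 7-point difference, 7% versus about 0%, would give 52. The sample size is not in dispute here; only the 60 is used below.

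Effect of reclassifying k patients in one arm = k / 60:

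- k = 1: 1/60 = 1.67 points, or 1.67/3 = 56% of the margin
- k = 2: 2/60 = 3.33 points, more than the margin

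These values assume equal arms of 60; simple randomization may give slightly unequal arms. They show how sensitive a trial of this size is to single classifications. They would be the same under perfect blinding, and they say nothing about how likely a misclassification is.

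**The case against.** The strongest reply is that recording is not judging. Adequacy, termination and intubation are decided in the room by clinicians who are meant to be blinded, and their endoscopic reports are collected. The arm is communicated by someone other than the endoscopist, both at assignment and at the reminder, so the sticker is not the only safeguard. The coordinator/investigator may be two people. The data collection sheet, the phone scripts and the consent pages are not in the supplied text and may settle some of this.

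Most of that stands, and it limits the point. A reader might infer that an unblinded person decides the primary outcome. The documents do not support that: they are silent on who classifies it. A reader might also infer that patients are never asked to keep their arm private. All that can be said is that the supplied text contains no such instruction.

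What the reply does not remove is that the plan nowhere says the blinded clinicians' entries, rather than the coordinator's, determine the composite. Nor does it separate the two tasks given to one role, or state any blinding for the aspiration follow-up.

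**Conclusion.** The concern holds as a gap in how the blinding is carried through to the outcome data. One role both learns the arm and records outcome fields, the classifier of a judgement-based composite is not named, and aspiration follow-up has no stated blinding. Bias is possible in either direction; nothing in the documents shows that it will occur.

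The size of the bias cannot be estimated. One patient in 60 is worth 1.7 points against the 3-point margin, and two in the same direction are worth 3.3. A reader might go further and say that about 4.5 primary events are expected (60 × 7% + 60 × 0.5% = 4.2 + 0.3). The documents do not support that: those rates are for increased residual gastric volume in users and non-users, and Sample Size Determination itself warns that they may not reflect the primary outcome. A reader might also assume that knowledge of the arm would count against continuing, but the protocol's own text gives reasons for either direction.

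The conclusion rests on the supplied text alone, with the scripts, consent pages and data collection sheet unseen. The change is worth making because it is cheap and removes an avoidable doubt about the primary result.

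**What to change.** 1. State that the blinded endoscopist and anesthesia provider enter or sign the in-procedure components (adequacy, premature termination, intubation due to stomach contents) and the residual-content fields at the end of the procedure. State that these entries, not the coordinator's, determine the outcome.
2. Store compliance and last-dose answers in a REDCap field that the procedure team cannot see. The question may be asked before sedation if the person asking does not enter or classify outcomes. Otherwise, ask it at the existing follow-up call after the aspiration answers have been saved. Asking straight after the procedure would mean questioning a recently sedated patient.
3. Have the one-week aspiration call or record review completed and saved by an existing study member before that person sees the arm. This component cannot be signed off in the procedure room, so it needs its own rule.
4. Add one sentence to the existing reminder call asking patients not to tell the procedure team their arm, if the script does not already contain it.

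Cost: about a minute of clinician time per case and some REDCap access set-up. No extra staff and no change to the sample size.

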- Occurrence of aspiration events requiring extended observation/monitoring, unplanned therapeutics, and/or hospital admission

Secondary Outcomes:

- Presence of any solid food
- Presence of moderate liquid content
- Increased RGC defined as any amount of solid content or $> 0.8 \text{ mL/Kg}$ of fluid content (measured from the aspiration/suction canister).
- Aspiration events up to 48 hours after endoscopy
- Differences in primary and secondary outcomes between different medications

Inclusion Criteria:

- Patients using incretin-based therapies at a stable dose for more than 1 month.
- Understand the study procedures and will be able to provide written informed consent to participate in the study.
- Patients scheduled for outpatient esophagogastroduodenoscopy (EGD), combined EGD and colonoscopy, endoscopic ultrasound (EUS), or endoscopic retrograde cholangiopancreatography (ERCP) under monitored anesthesia care (MAC) or moderate sedation.

Exclusion Criteria:

- Documented history of gastroparesis (based on a 4-hour solid-phase gastric emptying study)

- Known history of achalasia
- Surgical or genetically altered foregut anatomy
- Known gastric outlet obstruction or pre-procedure imaging suggestive of gastric outlet obstruction.
- Patients who did not follow the standard NPO (nil per oral) instructions.
- Patients who have planned endotracheal intubation (ETT) during their upper endoscopy procedure (EGD, EUS, or ERCP).
- Ongoing opiate use
- Unable or unwilling to give written consent

Randomization:

- Patients will be randomly assigned to either continue incretin-based therapy as prescribed (“continue” group) or to hold therapy as outlined in the ASA guidance recommendations (“hold” group).
- Simple randomization will be applied post-enrollment, utilizing REDCap serial numbers with pre-determined interventions (“continue” vs. “hold”). The randomization table of allocation will be completed by a statistician on REDCap to ensure concealed allocation.

Study Operation:

- The candidates for the study will be determined either during the gastroenterology clinic visit OR based on review of records by a member of the research team of patients scheduled for upper endoscopy, EUS, and ERCP cases three to four weeks in advance
- Patients’ invitation
 - For patients who are scheduled for the procedure through the gastroenterology clinic, the patient’s clinic provider will invite the patient for the study during the office visit or with a phone call.

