- An investigator or research coordinator will contact the invited candidates over the phone 2-4 weeks before the scheduled procedure. The study purpose, intervention, adverse events, and consenting process will be discussed over the phone. The encounter will be documented in the patient chart as a phone encounter.
- Subjects interested in the study will be provided with consent through MyChart Electronic consent or DocuSign with instructions to complete online consent signing.
- After all parties complete the consent, a randomization of the study intervention will be done through Redcap.
- A follow-up phone call will be made to communicate the instructions to the participants.

Rational for electronic consent (E-consent)

The study is not feasible with conventional consent, especially for open access procedures for the following reasons:

- The duration for participant involvement in the study is short, and the study intervention is only applied one week before the procedure, which would make it impractical to bring the patient for an extra encounter and would decrease the chance for enrollment.

- Many procedures are scheduled in an open-access fashion, which means that the patient is scheduled for the procedure by a provider other than the performing physician and/or from a different department.
- The intervention for the study must be completed one week before presenting to the procedure, which requires that the patient be enrolled before the procedure date.

Sample Size Determination:

- Previous retrospective studies indicate that 5-7% of GLP-1RA users have increased RGV compared to less than 0.5% in non-users.
- If there is a significant difference in favor of the experimental (“hold”) group of 7%, then 120 patients are needed (60 in each group) to be 80% certain that the upper limit of a one-sided 95% confidence interval (or equivalently a 90% two-sided confidence interval) will exclude a difference in favor of the standard group of more than 3% (the non-inferiority limit) using Farrington-Manning’s score test.
- Because estimates from previous retrospective studies are for the outcome of residual gastric volume, they may not accurately reflect our primary outcome, which is a more pragmatic and clinically useful outcome. Therefore, we plan to conduct an interim analysis at 20% recruitment and may adjust sample size if necessary, based on point estimates derived from the interim analysis.

Study Variables

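### For patients not reached by phone, the record review covers only emergency visits and admissions, which is narrower than the aspiration outcomes it is meant to capture

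*Combined protocol and SAP*

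**What the plan says.** The fourth component of the primary composite (Primary Outcomes) is "Occurrence of aspiration events requiring extended observation/monitoring, unplanned therapeutics, and/or hospital admission". The alternatives are joined so that any one is enough, and no care setting or time window is given. The Secondary Outcomes list adds "Aspiration events up to 48 hours after endoscopy", with no limit on severity or setting.

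The Study Operation section gives two routes to these events:

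- On the endoscopy day: "A research coordinator/investigator will confirm intervention compliance and record the variables of interest for the study".
- Afterwards: "A phone call to the patient within the first week after the procedure to follow up and exclude aspiration events". If the patient cannot be contacted, a team member is to "review patient records to identify any emergency department visits or hospitalizations related to a post-procedure aspiration event".

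No other section widens that review. Study Statistics says "For the primary outcome, an intention-to-treat analysis will be utilized" and gives no rule for a missing or partly ascertained outcome. It is also not stated how an unreached patient with a negative review is classified. The Study Variables section points to a data collection sheet that is not among the documents.

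**The concern.** The fallback search is narrower than the outcomes it serves. It would find an admission. It is not directed at unplanned treatment given outside an emergency department or hospital, or at a milder aspiration within 48 hours. The outcome definition is the same for everyone, but the chance of detecting an event depends on whether a phone call connects.

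The setting makes the gap plausible. Participants are outpatients, and the electronic-consent rationale notes that many are scheduled open-access, by a provider other than the performing physician or from another department. Care for a later respiratory complaint may well be sought away from the endoscopy team.

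Aspiration is one of the harms listed under Possible Harm to Subjects and Adverse Events, and outcome events go to the IRB after each monitoring meeting. An undercount would therefore affect safety reporting as well as the comparison. With few events expected, a single miscounted one can matter to the test.

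**Working it through.** **1. What each route can detect**

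| Event | Counts towards | Procedure-day record | Phone call | Fallback review |
|---|---|---|---|---|
| Inadequate examination, early termination, intubation | Primary | Yes | Not needed | Not needed |
| Aspiration managed on the procedure day | Primary, 48-hour secondary | Yes | Yes | Not needed |
| Post-discharge aspiration, emergency visit or admission | Primary if the treatment criterion is met; secondary if within 48 hours | No | Yes | Yes |
| Post-discharge aspiration treated in clinic, by phone or portal, or by prescription | Same | No | Yes | **No** |

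The gap is the last row, and only for patients whom the call does not reach.

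**2. The plan's own figure**

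Inputs from Sample Size Determination: "5-7% of GLP-1RA users have increased RGV compared to less than 0.5% in non-users"; margin 3 points; one-sided 5%; power 80%; Farrington-Manning test. Take hold p_H = 0.005 and continue p_C = 0.07. The restricted null estimates are 0.0658 and 0.0358.

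- s0 = √(0.0658×0.9342 + 0.0358×0.9642) = 0.310
- s1 = √(0.005×0.995 + 0.07×0.93) = 0.265
- n per arm = [(1.645×0.310 + 0.842×0.265) / (0.03 + 0.065)]² = 59.5, so 60 per arm and 120 in total

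This matches the stated size, so the calculations below use the same rates, margin and test. Expected events are 60×0.005 = 0.3 (hold) and 60×0.07 = 4.2 (continue), 4.5 in all.

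**3. Expected missed events**

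Missed per arm = 60 × event rate × share unreached × share of events that are post-discharge aspirations treated outside emergency department or hospital. The documents give neither share; the ranges 5-30% and 5-20% are assumptions.

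| Arm | Low | High |
|---|---|---|
| Continue (7%) | 60×0.07×0.05×0.05 = 0.01 | 60×0.07×0.30×0.20 = 0.25 |
| Hold (0.5%) | 60×0.005×0.05×0.05 = 0.001 | 60×0.005×0.30×0.20 = 0.018 |

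At the high end the observed continue rate falls from 7% to 0.07×(1 − 0.06) = 6.58%.

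**4. What one miss does to the test**

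z = [(x_H − x_C)/60 − 0.03] / SE, with SE from the restricted estimates under a true difference of 0.03; P is the lower tail.

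| Hold vs continue events | P (one-sided) | Non-inferior at 5% |
|---|---|---|
| 0 vs 2 | 0.023 | Yes |
| 1 vs 2 | 0.081 | No |
| 1 vs 3 | 0.0445 | Yes |
| 0 vs 4 | 0.006 | Yes |
| 1 vs 4 | 0.024 | Yes |
| 2 vs 4 | 0.068 | No |

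- Hold-arm miss: a true 1 vs 2 seen as 0 vs 2 turns not shown into shown.
- Continue-arm miss: a true 1 vs 3 seen as 1 vs 2 turns shown into not shown.
- Near the expected count: a true 1 vs 4 seen as 0 vs 4 changes nothing.

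At the plan's rates 4.2/4.5 = 93% of events fall in the continue arm. If the two shares are alike in both arms, most misses fall there too.

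**The case against.** A reader might infer that missed events are always scored as no event, that this biases the trial towards non-inferiority, and that one miss decides the result. The documents do not support that reading.

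- **Scoring.** No section says how an unreached patient with a negative review is coded, and the data collection sheet cannot be seen. Counting such a patient as event-free is the likely default, but it is an inference.
- **Direction.** At the planning rates nearly all missable events are in the continue arm, where a miss makes non-inferiority of holding harder to show. Equal undercounting shrinks the assumed advantage of holding towards zero.
- **Decisiveness.** A single miss reverses the conclusion at some counts (0 vs 2 against 1 vs 2) but not at 0 vs 4 against 1 vs 4, which is closer to what the plan expects.
- **Scope.** Inadequate examination, early termination, intubation and same-day aspiration are recorded on the day. If the primary aspiration component was meant as peri-procedural only, the gap falls mainly on the 48-hour secondary outcome. The text sets no such limit, but gives no post-discharge window for the primary component either.
- **Rank of the harm.** The protocol lists aspiration among several possible consequences and does not call it the main one.

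All of this stands, and it limits the point to a small ascertainment gap. It does not remove the mismatch: the stated search leaves out events that the stated outcomes include.

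**Conclusion.** The point holds as a minor one. For unreached patients the record review is narrower than the primary aspiration component and the 48-hour secondary outcome, so a post-discharge aspiration treated outside an emergency department or hospital would probably go uncounted. The effect is under-reporting of a named harm. The expected number of missed events is well below one, and the non-inferiority result could move in either direction. The sample size is not affected.

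The size rests on assumptions: the non-contact share and the share of events treated elsewhere are not in the documents, and the 7% and 0.5% rates describe increased residual volume, which the protocol itself says may not reflect the composite. The P values use the test named in the sample-size section.

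**What to change.** In Study Operation, replace the fallback with a review of all available records in the follow-up window, judged against the primary and secondary aspiration definitions: clinic and telephone encounters, portal messages, new prescriptions, imaging, emergency visits and admissions. Report by arm how many patients were assessed by record review only.

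It would be tempting to go further, coding patients with no later contact as unknown and counting hold-arm unknowns as events. That is not advised. Well outpatients often have no further contact, so uneventful recoveries would become missing data. At an assumed 10-20% non-contact, up to 6-12 of 60 hold patients could become events, whereas 2 against 4 already fails (P = 0.068). Such an analysis could not inform.

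The cost is a sentence or two in the protocol and a few more minutes of chart review per unreached patient, by the team member already assigned. Patient care is unchanged.

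### Randomisation follows consent directly, often weeks before the arms differ, so avoidable cancellations and eligibility changes fall after randomisation in an intention-to-treat set with no loss allowance

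*Combined protocol and SAP*

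**What the plan says.** The sequence is set out in two sections of the combined protocol and SAP.

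- **Telephone route (Electronic Consent operation).** Study staff "contact the invited candidates over the phone 2-4 weeks before the scheduled procedure". E-consent follows, then "After all parties complete the consent, a randomization of the study intervention will be done through Redcap", then a call giving the instructions.
- **Clinic route (Study Operation).** "Interested patients in the clinic setting will be given the option to complete a research encounter during the same day, including in-person consent if interested". REDCap entry and allocation come next, and "The patient will be informed about the intervention during the clinic visit by a study member (not the endoscopist) or over the phone". No maximum interval from clinic visit to endoscopy is stated.
- **When the arms differ.** The e-consent rationale says that "the study intervention is only applied one week before the procedure". The guidance that the hold arm follows, as summarised under Background, is that "patients on daily dosing hold incretin-based therapy the day of the procedure, and those on weekly dosing hold the medication a week before the procedure".
- **Later contact.** Under Study Operation, "A few days before the intervention, the patient will receive a call as a reminder of the intervention and instruction". This call comes after allocation.

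No step between consent and randomisation waits for the procedure to approach or rechecks eligibility. Study Statistics specifies intention to treat for the primary outcome. It has no rule for randomised patients whose endoscopy does not take place. Sample Size Determination asks for 60 per group and makes no allowance for losses.

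**The concern.** For one to three weeks on the telephone route, and possibly longer on the clinic route, a patient is randomised and knows the arm while both arms are doing the same thing. For daily dosing this period is longer still. Within it the procedure can be cancelled, the dose can change, opiates can be started, intubation can be planned, or imaging can suggest outlet obstruction. The last four bear directly on the inclusion and exclusion criteria.

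If these happened before randomisation, the patient would simply not enter the trial. Because they happen after it, the patient belongs to the intention-to-treat set, either with no outcome or as someone who no longer meets the criteria. The trial expects very few events, so an incomplete set matters more here than in a trial with a common outcome.

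**Working it through.** **1. The plan's own figure.** Inputs from Sample Size Determination: one-sided 5%, 80% power, 3-point limit, Farrington-Manning test. The pair of rates that gives 60 is hold 0.5% and continue 7%, the ends of the quoted retrospective rates.

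Power = Φ{[0.03 + (0.07 − 0.005) − 1.645·s0] / s1}, where s0 uses the rates restricted to a 3-point difference (6.58% and 3.58%) and s1 the assumed rates.

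- s0 = √(0.09604/60) = 0.0400
- s1 = √(0.07008/60) = 0.0342
- Power = Φ[(0.095 − 0.0658)/0.0342] = 80.4%

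The required number is 59.5, so 60 per arm and 120 in total. The stated size is reproduced with nothing to spare on this method. Expected events: 60 × 0.005 + 60 × 0.07 = 4.5.

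**2. Losses by lead time.** The documents give no rate, so a constant weekly loss h is assumed: 5%, range 2-8%. Losses among 120 = 120 × [1 − (1 − h)^w], with w in weeks. The comparator of 10 days is about one week plus a few days' notice.

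| h per week | 10 days | 2 weeks | 4 weeks | Avoidable (2 weeks, 4 weeks) |
|---|---|---|---|---|
| 2% | 3.4 | 4.8 | 9.3 | 1.3, 5.9 |
| 5% | 8.5 | 11.7 | 22.3 | 3.2, 13.8 |
| 8% | 13.5 | 18.4 | 34.0 | 5.0, 20.6 |

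Only the last column counts against the present timing: about 3-14 patients at 5%, and 1-21 over the whole range. Longer clinic-route intervals would add to it.

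**3. Effect on power, two methods.**

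*Asymptotic (step 1 formula at reduced n).*
- 5% loss (57 per arm): 78.3%
- 10% loss (54 per arm): 76.2%
- 20% loss (48 per arm): 71.3%

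*Exact enumeration of the same test, averaged over binomial retention, at h = 5%.*
- No loss: 92.3%
- 10 days (7.1% loss): about 89%
- 2 weeks (9.75% loss): about 87%
- 4 weeks (18.55% loss): about 80%

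The methods differ in level but agree in direction. The exact figures do not fall smoothly. At 54 per arm power is 91.0%, and at 53 it is 79.8%, because with no hold-arm events the test then needs two continue-arm events instead of one. That step comes from the small counts and is not a cost of timing as such.

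**The case against.** **The lead time is inferred.** The 2-4 weeks is the window for the telephone contact, and e-consent must be completed first, so the true gap may be shorter. This stands as a caution. Still, no later point for randomisation is set, and the clinic route allows the arm to be given at the visit.

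**Much of the loss is not avoidable.** Last-week cancellations and fasting failures on the day follow randomisation in any case. A rescheduled patient, or one who starts opiates or changes dose, can still have an endoscopy and supply an outcome under intention to treat. This stands. It is why only the increment over about 10 days is counted, and it means that the assumed rate overstates the loss if many procedures are merely moved.

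**Early allocation has a use.** A reader might infer that it gains nothing, since a call is planned shortly before the intervention. The plan provides two contacts, an instruction and a separate reminder, and a patient on weekly dosing must know the arm before the dose in question. That inference is not supported, and the reminder should be kept.

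**A reversal by hidden events is not supported.** With 60 per arm, 0 hold against 4 continue events meets the limit and 2 against 4 does not. A reader might infer that two unseen hold-arm events among the losses could reverse the result. Every component of the primary outcome arises at or after endoscopy, so a cancelled patient has no hidden event.

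**Other remedies exist.** A rule for randomised patients without endoscopy and a loss allowance (120/0.90, rounded up to 134, for 10% loss) are direct gaps that could be closed without moving randomisation. They are worth adding, but they would not prevent the losses.

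**Conclusion.** The concern holds as a matter of timing. Randomisation is placed earlier than the intervention needs, and what happens in the gap is carried into an intention-to-treat set with no loss allowance. The sure cost is precision and completeness. Against allocation at about 10 days, the exact power at 5% per week is lower by roughly 2 points at 2 weeks and 9 points at 4 weeks, ending near the stated 80%. On the asymptotic method any loss of 5% or more already puts power below 80%.

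These sizes rest on an assumed weekly loss rate, on losses being permanent, and on the rates of 0.5% and 7%. A reader might also infer bias, because patients know their arm early. Withdrawal related to arm is possible, but nothing in the documents shows it, and before the arms diverge cancellations are likely to be largely unrelated to allocation. The point is a worthwhile and inexpensive improvement and does not invalidate the design.

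**What to change.** Keep consent where it is. On both routes, open REDCap randomisation only at the instruction call, timed as late as practicable before the first dose that the two arms treat differently. At that call, first reconfirm the procedure date, stable dose, opiate use, planned airway and any new imaging; then randomise and give the instruction. Keep the later reminder call. Count the 120 from randomisation, so that patients lost earlier are replaced without entering the intention-to-treat set.

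The cost is a wording change and one REDCap step moved. Clinic patients who would have been told their arm at the visit are told by telephone instead, an option that the plan already provides. Patients have shorter notice of their arm, and some consented patients who cannot be reached are never randomised; because that happens before allocation, it cannot unbalance the arms. If the instruction call must sit some days ahead of the reminder, the lead time will exceed 10 days and the gain over a two-week contact will be smaller.
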